From a biological perspective, recent data suggest that ADT may not provide sufficient control of the primary tumor, which may act as a continued source for additional metastatic spread and resistant clonal selection.¹³⁻¹⁵ While there is evidence that demonstrates prostate cancer has significant heterogeneity within the multiple foci of tumors with a gland, molecular and cytogenetic data show that multiple metastases within the same patient are clonally related¹⁶⁻¹⁸ suggesting that metastatic clones may arise from a selective advantage of individual clones and that further systemic therapies may select for cells with varying malignant potentials. Therefore, definitive treatment of the primary tumor may also improve outcomes by removing a major source of spread and thereby increasing freedom from local and distant progression, delaying time to castrate resistance and prolonging time to fatal metastatic burden, thus resulting in prolongation of overall survival.

In this context, it will be important to develop a potential imaging biomarker for assessing response to SST which can potentially differentiate responders vs non-responders early in the course of treatment. It is possible that SST might significantly benefit only a subset of patients and imaging biomarker could allow risk stratification and possible incorporation of alternative therapies at a time when they would be expected to be most effective.

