Primary objective: Evaluate metabolic response by 18F-fluciclovine PET qualitatively and semi-quantitatively with standardized uptake values (SUV) following standard systemic therapy at 22-28 weeks (+/- 4 weeks) and correlate the findings with size changes as defined by conventional imaging and PSA response.

Secondary objectives:

- 1. To correlate pelvic 18F-fluciclovine PET imaging findings with pathologic findings at radical prostatectomy and pelvic lymph node dissection to determine 18F-fluciclovine PET imaging sensitivity and specificity for pelvic lymph node cancer involvement.
- 2. To evaluate 18F-fluciclovine PET imaging response and its correlation with progression free survival (defined by PCWG2 criteria)
- 3. To determine if sites of progressive disease develop at the initial/prior site (diagnostic site) of metastases or in newly developed sites at the time of metastatic progression.
- 4. To evaluate metabolic response by 18F-fluciclovine PET semi-quantitatively with target to blood pool ratio (TBR) following SST at 22-28 weeks (+/- 4 weeks), and correlate the findings with size changes as defined by conventional imaging and PSA response.

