5.0 Research Design and Methods

5.1 Study Design

A prospective pilot study will consist of eligible patients referred from genitourinary multidisciplinary care center at the University of Texas at MD Anderson cancer Center. All eligible patients scheduled to receive SST for up to 28 weeks will be enrolled, and initial 18F-fluciclovine PET CT will be performed within four weeks before initiation of systemic therapy. The patient will receive SST for up to 28 weeks, and 18F-fluciclovine PET CT will be repeated within four weeks following SST. 18F-fluciclovine PET CT will be performed as per the standard institutional protocol (Appendix C.). Blinded image interpretation will be made by radiologists and nuclear medicine physician. All scans will be interpreted independently by two physicians. Areas of focal tracer uptake will be localized with the companion CT and classified as lesions of the prostate, pelvic nodes, extrapelvic nodes, visceral, and bone lesions. Three- dimensional regions of interest will be placed in areas of tracer uptake, and measures of 18F- fluciclovine avidity will be recorded; the measures include SUVmax (body weight), metabolic tumor volume (MTV; volume of tumor [cm3] with SUV >42% of SUVmax), SUVmean (within the MTV), and total lesion avidity (TLA; calculated as MTV x SUVmean). A background SUVmax will be documented for each examination. On both pretreatment and posttreatment scans, the lesion SUVmax will be corrected for the background as follows: corrected SUVmax = lesion SUVmax background SUVmax. When the correct SUVmax is less than 0, 0 will be recorded. Similar corrections will be made for SUVmean. When the corrected SUVmax and the corrected SUVmean are 0 on posttreatment scans, MTV and TLA will also be recorded as 0. The percentage of change in the 18Ffluciclovine SUVmax after therapy will be calculated as follows: [(pretreatment corrected SUVmax posttreatment corrected SUVmax)/pretreatment corrected SUVmax] x 100. Similar calculations will be performed for SUVmean, MTV, and TLA.

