5.2 Reference standard

We will calculate tumor response by using RECIST 1.1 for visceral, bone and lymph node metastasis.²⁵ Primary tumor within the prostate gland will be assessed based on percent reduction in tumor size, changes in restricted diffusion and ADC value on mp pelvic MRI.²⁶⁻²⁸ In patient with available pathological specimen following prostatectomy and pelvic LN dissection, the pathologic response will be used to assess tumor response as well as identification of involved lymph nodes to assess for specificity and sensitivity of F18 Fluciclovine to detect occult lymph node involvement. Patients will be dichotomized by PSA measurement is taken at six months, PSA \leq 4 and PSA > 4.²⁹

Response assessment **Evaluation of Target lesions** Complete Response (CR) Disappearance of all target lesions. Any pathological lymph nodes (whether target or non-target) must have reduction in short axis to <10 mm. Partial Response (PR) At least a 30% decrease in the sum of diameters of target lesions, taking as reference the baseline sum diameters. At least 17% increase in median ADC value within the tumor on DWI MR images. Progressive Disease (PD): At least a 20% increase in the sum of diameters of target lesions, taking as reference the smallest sum on study (this includes the baseline sum if that is the smallest on study). In addition to the relative increase of 20%, the sum must also demonstrate an absolute increase of at least 5 mm. (Note: the appearance of one or more new lesions is also considered progression). Stable Disease (SD): Neither sufficient shrinkage to qualify for PR nor sufficient increase to qualify for PD, taking as reference the smallest sum diameters while on study. Evaluation of non-target lesions Complete Response (CR): Disappearance of all non-target lesions and normalization of tumor marker level. All lymph nodes must be non-pathological in size (<10mm short axis). Non-CR/Non-PD Persistence of one or more non-target lesion (s) and/or maintenance of tumor marker level above the normal limits. Progressive Disease (PD): Unequivocal progression (see comments below) of existing non-target lesions. (Note: the appearance of one or more new lesions is also considered progression).

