5.4 Study Calendar (Accrual process)

Visits	Activities	Site/Person involved
Initial clinic visit	Determination of eligibility	GU multidisciplinary center
Imaging visit	Standard of care Bone scan	Diagnostic Imaging
Imaging visit	The standard of care CT abdomen	Diagnostic Imaging
Imaging visit	The standard of care pelvic MRI with endorectal coil	Diagnostic Imaging
Imaging visit	Research 18F-fluciclovine PET CT	Diagnostic Imaging

5.5 Pre-test/study evaluation

Patients with metastatic prostate cancer are seen and evaluated at genitourinary multidisciplinary care center of MDACC. Based on the past clinical volumes, we are expected to see 2-4 metastatic prostate cancer patients per month. This center is staffed by clinical faculty from urology, medical oncology, and radiation oncology departments. Before enrollment, patients will be seen in genitourinary multidisciplinary center in consultation with a medical oncologist, urologist, and radiation oncologist to ensure eligibility.

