5.8 Post Systemic Therapy-Imaging Visits

Patients will return following 22-28 weeks (+/- 4 weeks) of SST for follow-up imaging studies which will include MDP Bone scan, CT abdomen, MP PELVIC MRI AND 18F-FLUCICLOVINE PET CT.

5.9 Criteria for Removal from Study

Subjects must be withdrawn from the study for the following reasons:

- 5.9.1 The patient withdraws consent
- 5.9.2 The patient cannot complete all imaging tests within 30 days of time frame.
- 5.9.3 Study completed

5.10 Innovation:

This is to our knowledge the first study of using 18F-fluciclovine PET CT in the assessment of therapy response in prostate cancer. Although glucose metabolism is recognized as a key metabolic pathway for imaging, amino acid metabolism is emerging as a promising pathway for

tumor imaging.^{30,31} Recent studies with ¹⁸F-Fluciclovinehave shown that this tracer can accurately detect prostate cancer and regional lymph node metastases with better specificity and sensitivity.³²⁻ ³⁴ 18F-fluciclovine have also been tried in breast cancer with positive results. A pilot study evaluated the ability of ¹⁸F-fluciclovine avidity to determine neoadjuvant therapy response in 24 breast cancer patients, using histology after definitive surgical management as the gold standard.³⁵ Changes in ¹⁸F-fluciclovine avidity strongly correlated with the percentage of reduction of tumor seen on pathology.³⁵ Motivated by these prior studies, we propose to evaluate the ability of 18F-fluciclovine avidity to determine neoadjuvant therapy response in M1PCa. In addition to establishing the importance of tumor response assessment with novel radio tracers, this study has the potential to combine with pelvic MRI and whole-body MRI to study high risk and metastatic prostate cancer. Also, the knowledge gained from this research will be used to design and test the utility of PET-MRI with novel tracers such as 18F-fluciclovine and PSMA. The culmination of the pilot studies will be an extramural application to conduct a multicenter trial.

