Kaplan-Meier method will be used to estimate progression free survival (PFS). Log-rank test will be used to compare PFS between imaging response groups. Frequencies will be estimated for different types of metastatic progression sites. Other statistical analyses will be carried out as appropriate.

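### PFS is compared between groups known only after the post-treatment imaging, with no time origin or landmark, so early progression could count as an outcome of the group it helped to assign

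*Combined protocol and SAP*

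**What the plan says.** - Secondary objective 2 (section 3.0): "To evaluate 18F-fluciclovine PET imaging response and its correlation with progression free survival (defined by PCWG2 criteria".
- The PFS plan in section 6.0 is Kaplan-Meier estimation followed by one comparison: "Log-rank test will be used to compare PFS between imaging response groups". No start date, landmark, time-dependent analysis or rule for early progression is given. The imaging response groups are not defined either. The nearest text is the Youden cut-off on SUVmax change or size change, and both changes need the post-SST imaging.
- Section 5.1 defines PET response as a change from the pretreatment to the posttreatment scan, and says of timing: "The patient will receive SST for up to 28 weeks, and 18F-fluciclovine PET CT will be repeated within four weeks following SST".
- Section 5.8 brings patients back after 22-28 weeks (+/- 4 weeks) of SST for "follow-up imaging studies which will include MDP Bone scan, CT abdomen, MP PELVIC MRI AND 18F-FLUCICLOVINE PET CT".
- Section 5.2 (RECIST 1.1, the reference standard for response) allows progression to be called on that imaging: "the appearance of one or more new lesions is also considered progression".

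**The concern.** The grouping variable is measured months after treatment starts, and conventional imaging that can show progression is repeated in the same window. Suppose PFS were counted from SST start. A patient whose disease grows under SST could then be classed as a PET non-responder because of that growth, and contribute a PFS event because of the same growth. The two curves would separate before or at the scan even if PET response said nothing about what follows.

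That matters because the rationale in section 2.0 looks forward from the scan: an "imaging biomarker could allow risk stratification and possible incorporation of alternative therapies". Such use needs evidence that PET response separates later outcomes among patients who have not yet progressed. Section 6.0 as written does not ensure that the log-rank test addresses that question.

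**Working it through.** **1. When the group is known.** By section 5.8 the earliest post-SST scan is at 22 - 4 = 18 weeks and the latest at 28 + 4 = 32 weeks. Section 5.1 sets no lower bound on SST duration.

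**2. The plan's own figures.** There is no event count, hazard ratio or power for PFS. The only power stated is 83% for the AUC (0.76 against 0.50; 28 responders, 13 non-responders). With Hanley-McNeil variances the standard errors are 0.0981 (null) and 0.0756 (alternative). Power is then Φ[(0.26 - 1.96 × 0.0981)/0.0756] = Φ(0.90), about 81.5%. That is close to the stated figure, and this point does not touch it.

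**3. Mechanism by hand.** Assume 10% early progression, 90% of early progressors PET non-responders, and 25% non-response among the rest.
- Early progressors: 41 × 0.10 = 4.1, of whom 0.90 × 4.1 = 3.69 are in the non-response group.
- Size of that group: 3.69 + 0.25 × 36.9 = 12.9, or 31.5% of 41. Its share at risk falls from 31.5% to 25% as the early events occur, averaging 28.25%.
- Excess early events: 3.69 - 4.1 × 0.2825 = 2.53.
- Variance with 27 events in all: 4.1 × 0.2825 × 0.7175 + 22.9 × 0.25 × 0.75 = 0.83 + 4.29 = 5.12.
- Shift in the log-rank statistic: 2.53/√5.12 = 1.12, so rejection is about Φ(-0.84) + Φ(-3.08) = 0.20.

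Simulation gives 24%. The hand calculation fixes the number of early progressors at its mean.

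**4. Simulation.** The inputs not in the documents are assumptions: n = 41; PET at week 26; half of early progressions dated over weeks 12-26 and half at the last conventional study, 0-30 days after the PET; 25% PET non-response among other patients; equal exponential post-scan times (mean 80 weeks); censoring 52-104 weeks after the PET; 4,000 trials per setting. Each range covers 50% to 90% of early progressors being PET non-responders.

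| Early progression (expected of 41) | From SST start | Landmark at PET | Landmark at last study |
|---|---|---|---|
| 5% (2.05) | 7.9-12.0% | 6.4-8.2% | 5.3-5.9% |
| 10% (4.1) | 10.8-24.2% | 8.0-12.9% | 5.4-5.8% |
| 15% (6.15) | 12.8-36.9% | 8.9-18.1% | 5.7-7.2% |

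At 2.5% (about one patient) rejection from SST start is 6-9%. A repeat with 3,000 trials gave 37.8% at the top of the last row, hence the overall range of about 6-38%.

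**5. What moves the result.**
- Grouping unrelated to early progression: 4.8-6.5% from SST start, so no inflation.
- Half of early progressors never scanned a second time: 6-9%, 7-13% and 8-20% at 5%, 10% and 15%.
- All early progressions dated before the PET: a PET-date landmark gives about 6%.
- All dated after the PET, 90% non-responders: a PET-date landmark gives 11.4%, 23.7% and 35.9%, about the same as starting at SST.
- A fixed landmark 30 days after the PET works when all studies fall within 30 days. If they spread over 8 weeks (90% non-responders, 10-15% early progression), it rejects in about 8-18%, against 5-6% for the last-study landmark.

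**6. Cost of the landmark.** From SST start there are about 26, 27 and 28 events at 5%, 10% and 15%. The last-study landmark loses 2-3, 4-5 and 6-7. With an assumed post-scan hazard ratio of 2.5, 10% early progression and 50% of early progressors non-responders, rejection falls from about 68% to 57-59%. Part of the 68% is the concurrent association.

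**The case against.** The strongest reply has five parts.

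- **The bias is conditional.** The documents do not say PFS starts at SST start. They define it by reference to PCWG2, whose content is not reproduced. This stands. A reader might infer that the plan commits to a biased analysis; the text supports only that the origin is open and nothing rules the problem out.
- **Two progression rules.** Section 5.2 uses RECIST 1.1 and PFS uses PCWG2, with no statement of how far they overlap. This stands as a limit. How often one finding would both assign the group and supply the event cannot be known from the documents.
- **The objective says correlation.** In the simulation PFS from SST start really does differ between groups; only the post-scan hazards are equal. Rejection is therefore not a false positive for objective 2 read literally. This stands too: the percentages measure how often a concurrent association could be mistaken for post-scan prognosis, which is the question section 2.0 raises.
- **Scheduling.** It is tempting to say that a PET-date landmark must fail because the studies fall on different days. Section 5.4 does list separate imaging visits (for example "The standard of care pelvic MRI with endorectal coil"), but its heading concerns accrual and it lists one PET. The removal criterion in 5.9.2, "The patient cannot complete all imaging tests within 30 days of time frame", may refer to the 30-day baseline rule in 5.7. The spread of the post-SST studies is therefore uncertain. That favours a landmark that does not depend on it.
- **Importance.** This is a secondary, unpowered comparison in a pilot. That limits the weight of the point. It does not remove it, since the repair is only wording.

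**Conclusion.** The concern holds in conditional form. The log-rank comparison uses groups known only after the post-SST imaging, and neither a time origin nor a rule for progression found by then is stated. If the clock started at SST, a significant result could reflect disease already evident at the scan.

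The 6-38% range is conditional on assumed rates of early progression, linkage to PET non-response and follow-up. It is not an estimate of the error rate in this trial, and the excess disappears if nobody progresses by the scan or if grouping is unrelated to early progression. Confidence is medium: the gap in the text is clear, its effect here is not. The change is worth making because it is cheap.

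**What to change.** In section 6.0, for the log-rank comparison by imaging response:

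- Set time zero at the date of the last study in the post-SST imaging set (PET, bone scan, CT, MRI), and include patients free of PCWG2 progression through that whole set.
- Report separately, by PET group where known, those who progressed at or before that date. Count those without a second PET as far as consent allows (5.9.1).
- Label the comparison exploratory.
- Keep Kaplan-Meier PFS from SST start, if wanted, as a description of the cohort.

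Do not offer a fixed 30 days after the PET as equivalent. It works only if every post-SST study is completed within 30 days of the PET, and 5.9.2 does not clearly say so.

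The change is to analysis wording only, with no added visits or scans. The price is the loss of events and power shown in the working, and a result that applies only to patients progression-free at the landmark. The comparison also then depends wholly on follow-up after the scan, for which no schedule is stated.

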6.0 Statistical Considerations

Objectives, Endpoints, and Study Design

The primary objective of this prospective study is to evaluate the ability of 18F Fluciclovine PET CT to determine the therapeutic response to SST. All eligible patients will be imaged by 18F Fluciclovine PET CT before and after treatment. Treatment responders were defined as the posttreatment PSA level <= 4.0 ng/mL, and >4.0 ng/mL for non-responders. The primary endpoint is the percentage change of 18F-fluciclovine SUVmax. Secondary endpoints include the size changes defined by conventional imaging; TBR; sensitivity, specificity, positive predictive value (PPV), and negative predictive value (NPV) when comparing 18 F Fluciclovine PET CT imaging findings with pathologic findings; progression free survival defined by PCWG2 criteria; and the types of metastatic progression sites. The accuracy of using the percentage change of 18F- Fluciclovine SUVmax to discriminate treatment responders from non-responders is evaluated using Receiver Operating Characteristic (ROC) curve analysis.

Sample Size and Power Calculation

We wish to enroll 41 evaluable patients. With an overall sample size of 41 and an estimated 70% response rate, we expect approximately 28 responders and 13 non-responders. With these numbers, we will have 83% power to detect a difference of 0.26 between the area under the ROC curve (AUC) under the null hypothesis of 0.50 and an AUC under the alternative hypothesis of 0.76 using a two-sided z-test at a significance level of 0.05. Considering a drop-out rate of 10%, the total sample size required is 45.

Analysis Plan

Patient characteristics and clinical outcomes will be summarized using frequencies, mean, standard deviation, median, and range. Accuracy of predicting responders using the percentage changes of SUVmax or the size changes by conventional imaging will be analyzed by ROC curves. AUC will be compared using the nonparametric method described by Delong (1988). Optimal cut- off points for dichotomizing the percentage changes of SUVmax or the size changes will be selected by maximizing the Youden's index. Dichotomized values will be compared using the McNemar's test. Sensitivity, specificity, PPV, and NPV to correlate dichotomized 18 F Fluciclovine PET CT imaging findings with pathologic findings will be estimated along with 95% confidence intervals.

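### For secondary objective 2, the only PFS test named compares undefined response groups; no named analysis uses the size of the SUVmax change or estimates the strength of the association

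*Combined protocol and SAP*

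**What the plan says.** Section 3.0 gives secondary objective 2 as: "To evaluate 18F-fluciclovine PET imaging response and its correlation with progression free survival (defined by PCWG2 criteria").

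The PET measure is continuous. Section 5.1 defines the percentage fall in background-corrected SUVmax, and Section 6.0 states: "The primary endpoint is the percentage change of 18F-fluciclovine SUVmax". Corrected values have a floor ("When the correct SUVmax is less than 0, 0 will be recorded"), so the fall cannot exceed 100% and men may tie there.

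For PFS, the Analysis Plan in Section 6.0 names Kaplan-Meier estimation and one test: "Log-rank test will be used to compare PFS between imaging response groups". It does not say what the groups are. The only rule for grouping SUVmax change stands earlier in the same plan: "Optimal cut- off points for dichotomizing the percentage changes of SUVmax or the size changes will be selected by maximizing the Youden's index". It is not tied to the PFS comparison. The plan ends with an open clause: "Other statistical analyses will be carried out as appropriate".

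No Cox model, hazard ratio or confidence interval is named for PFS. No PFS event count, follow-up time or power is stated. The size figures are "We wish to enroll 41 evaluable patients" and an "estimated 70% response rate, we expect approximately 28 responders and 13 non-responders"; the latter is the PSA split, not a PET split.

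**The concern.** A log-rank test between groups ignores how large the change was within a group. Under a two-group split, a man whose fall is just short of the cut counts the same as a man with no fall at all. The plan does use SUVmax change as a continuous variable for the ROC analysis, so the measure is available; it is left out only for PFS.

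Section 2.0 says there is as yet no evidence linking change in fluciclovine avidity to patient outcomes, and objective 2 is the one objective that relates PET response to a man's later course. Section 5.10 says the pilot work should lead to a multicenter application. A p-value from groups whose cut was chosen in these same data gives that application little to build on; a hazard ratio per unit of change, with its interval, gives more. With 41 men and an unknown number of events, information lost through grouping is also hard to replace.

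**Working it through.** **1. The plan's own figure.** The only power stated is 83% for AUC 0.76 against 0.50, two-sided 5%, with 28 responders and 13 non-responders. Using power = Φ((0.26 − 1.96·SE₀)/SE₁) with binormal variances gives 82.9% (Hanley-McNeil variances give 81.5%). The figure reproduces, but it concerns the ROC test and says nothing about PFS.

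**2. Information kept by a two-group split.** If the log hazard is linear in the change x, a split d keeps the share r = corr(x, d)². For normal x with proportion p on one side and cut z_p, r = φ(z_p)²/[p(1 − p)].

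| Split | r | Loss | 41 men count as |
|---|---|---|---|
| 50/50 | 0.637 | 36.3% | 26.1 |
| 28/13 | 0.586 | 41.4% | 24.0 |
| 70/30 | 0.576 | 42.4% | 23.6 |
| 80/20 | 0.490 | 51.0% | 20.1 |

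**3. Other shapes.** The cap at 100% makes a normal shape doubtful. The loss, 1 − corr(x, d)², at the 50/50 and 70/30 splits respectively:
- uniform: 25% and 37%
- 30% of men piled at the maximum: 35% and 29%
- t with 5 df: 46% and 50%
- left-skewed exponential: 52% and 38%

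This gives a working range of about 25-52%. It is not a bound: a 90/10 split of a normal predictor loses 66%.

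**4. Where the cut may fall.** The Youden cut is chosen from the data. In simulation with AUC 0.76 and 41 men, the share above it averaged 57% (5th to 95th percentile 32% to 80%), so 70/30 cannot be assumed.

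**5. Power if the effect is graded.** Event counts and hazard ratios are assumptions, because the plan gives none. The large-sample approximation is Φ(√(D·r)·ln HR − 1.96), with r = 1 for the continuous test. For D = 24 and HR 1.8 per SD (ln 1.8 = 0.588):
- continuous: √24 × 0.588 = 2.88; 2.88 − 1.96 = 0.92; power 82%
- log-rank at 70/30: √(24 × 0.576) × 0.588 = 2.18; 2.18 − 1.96 = 0.22; power 59%

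The approximation flatters the continuous test in a sample this small, so simulation is the better guide:

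| Setting (41 men) | Continuous Cox | Log-rank |
|---|---|---|
| HR 1.8 per SD, about 24 events, 70/30 | 75% | 57% |
| Same, about 25 events | 76% | 60% |
| Same, about 26 events | 79% | 60% |
| HR 1.8, 30-50% of men tied at a 100% fall | 73-76% | 58-59% |
| HR 1.5, about 23 events, Youden cut | 45% | 31% |
| HR 1.75, about 23 events, Youden cut | 71% | 50% |
| HR 2.0, about 23 events, Youden cut | 87% | 66% |

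**6. False positives.** Simulated type I error was 5.2-5.7% for the continuous test and 5.7-6.5% for the log-rank test at the Youden cut. The gain in power is not bought with extra false positives.

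**7. Power if the effect is a step.** With HR 3 exactly at a 70/30 cut and about 25 events, the log-rank test has about 78% power and the continuous test about 47%. A second run with about 26 events gave 77% against 50% (53% on ranks). The ordering reverses.

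**The case against.** The strongest reply is that a group comparison fits the purpose. Section 2.0 wants a marker that separates responders from non-responders, objective 2 speaks of imaging response, and a log-rank test by response group answers that. If PFS really changes at a threshold, step 7 shows that the log-rank test is the better one. This stands as a reason to keep the log-rank test. It is not a reason to rely on it alone: the documents give no prior threshold, the only cut-off rule is tuned to PSA rather than PFS, and step 7 favours the log-rank test by placing its cut exactly at the step.

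A second reply is that the closing clause leaves room for a Cox model. It does, but it prespecifies nothing, and a model chosen after seeing the data would be post hoc.

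A third is that the PFS groups need not be two. That is correct. Section 3.0 allows qualitative assessment and Section 5.2 lists several response categories. A reader might infer that the plan expressly dichotomizes SUVmax change for PFS; the text does not say so. The Youden split is the natural reading, and the missing definition is itself part of the point.

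Last, PFS is a secondary objective of a pilot with no PFS power claim. That limits the weight of the point, but the remedy is cheap.

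**Conclusion.** The point holds as a modest improvement to the plan. The one PFS test named compares undefined groups, and nothing named uses the size of the SUVmax change or estimates its association with PFS. If the effect is graded, the cost of a two-group split is roughly 25-52% of the information, or about 75% power against 57-60% in the assumed scenario of 41 men, about 24 events and HR 1.8 per SD.

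Three stronger readings are tempting and are not supported:
- **That this trial loses 36-42%.** That range needs a normal predictor, a log-linear hazard and a split between 50/50 and 70/30. The 70% in the plan is the PSA response rate, and the fall is capped at 100%.
- **That a real association would probably be missed because of the split.** At HR 1.8 the log-rank test still finds it in 57-60% of trials. At HR 1.5 with about 23 events both tests usually miss it (69% and 55%).
- **That grouping is the largest avoidable loss of power, or that the log-rank test should be only a display.** Nothing in the plan allows the first comparison, and step 7 speaks against the second.

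No figure stated in the plan is wrong.

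**What to change.** In the Analysis Plan of Section 6.0:

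1. Name, as the main analysis for objective 2, a Cox model for PFS with patient-level percentage change in SUVmax as a continuous covariate. Report the hazard ratio with its 95% CI.
2. Fix the form (raw or rank) and the scaling (for example per SD or per 25 points) in advance. Heavy ties at a 100% fall are a reason to consider ranks, but the choice should not wait for the data.
3. State how lesion values are combined into one value per man. Section 5.1 measures SUVmax by lesion, and the ROC analysis needs the same definition.
4. Keep Kaplan-Meier curves and the log-rank test as a supporting analysis, and state that the imaging response groups are those formed by the Youden cut-off on SUVmax change.

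The cost is a few sentences and no new data. The downside is that a monotone (log-linear or rank) effect is assumed, and the main test is weaker than the log-rank test if the true effect is a step at the cut. Keeping the log-rank test as support covers part of that risk.
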